1.2.1.1 Clinical Pharmacology

Plasma exposure of balovaptan increased in a greater than dose-proportional manner following single doses of 0.5 to 76 mg, whereas an approximately linear increase in exposure was observed after repeated dosing with 12 to 52 mg once daily (QD) for 14 days.

Balovaptan was rapidly absorbed with a median time to maximum observed plasma concentration (t_{max}) between 1 and 4.5 hours after administration of single doses in fasted state and between 3 and 4 hours following multiple dosing in fed state. Steady state was achieved after approximately 7 days, with an accumulation of approximately 4-fold after 12 mg QD and 2-fold after 52 mg QD; the mean apparent elimination half-life after the last dose (Day 14) was approximately 46 hours. Food had no relevant effect on the overall plasma area under the plasma concentration-time curve (AUC) of balovaptan.

In the human mass balance study (Study BP29279), an almost complete absorption of the study drug was observed within the first 72 hours following administration.

In plasma, steady state exposure to the [REDACTED] metabolite M3 was similar to or slightly higher than that of balovaptan and exposure to the [REDACTED] metabolite M2 was lower than that of parent. M3 and M2 qualify as major metabolites in plasma.

[REDACTED]

[REDACTED]

[REDACTED]

[REDACTED]

Hepatic metabolism was found to be the major pathway of elimination with the primary route of excretion via urine (approximately 53% of the material recovered, mostly

composed of metabolites). A further 30% of the administered dose was recovered in feces. The majority of excretion occurred within the first 7 days.

There was no clinically/statistically relevant PK interaction with the P-gp substrate risperidone, one of only 2 approved medications for ASD symptoms in the US, and fluoxetine, a weak CYP3A4 inhibitor often used to treat associated symptoms of ASD. Administration of a single dose of balovaptan 12 mg in combination with itraconazole, a strong CYP3A4 inhibitor, resulted in an increase in the exposure of balovaptan by 36% for maximum observed plasma concentration (C_{max}) and an approximately 3.1-fold increase for area under the concentration curve from time 0 to 120 hours (AUC_{0-120h}).

[REDACTED]

[REDACTED]

[REDACTED]

[REDACTED]

[REDACTED]

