3. STUDY DESIGN

3.1 DESCRIPTION OF THE STUDY

This study will be a non-randomized, open-label, parallel group, two-treatment study in healthy volunteers to investigate the absolute oral bioavailability of balovaptan. The study will be conducted at 1 site in the Netherlands.

Screening

Screening will be conducted up to 28 days prior to admission to the clinical research unit (CRU).

In-Clinic Confinement

Subjects will be in the CRU for 2 study periods. In both periods, subjects will be admitted on Day -1 (the day before dosing begins). Day 1 will be the first day of dosing. In Period 1, subjects will be discharged on Day 10 after all assessments have been completed. There will be a wash-out period of 14 days between Day 1 of Period 1 and Day 1 of Period 2.

Subjects will be readmitted to the CRU for a second in-house period on Day 14 of Period 1 (Day -1 of Period 2) to begin Period 2. Day 1 will be the first day of dosing. In Period 2, subjects will be discharged in the morning of Day 19.

During the in-house stays and screening and follow-up visits, subjects will undergo assessments as outlined in the schedule of activities ([Appendix 1](#)), including assessments of AEs and concomitant medications, vital signs, electrocardiograms (ECGs), clinical laboratory evaluations, and blood sampling for PK evaluations. ■

Dosing

Two cohorts of 8 subjects each will be included in the study. The 2 cohorts will receive the following treatment regimens:

Cohort 1

Period 1:

- Day 1: a single oral dose of 10 mg balovaptan after at least 10 hours of fasting, followed 1.25 hours later by a 15-minute intravenous (IV) infusion of [¹³C]-labeled balovaptan 0.1 mg.

Period 2:

- Day 1 to Day 14: oral doses of 10 mg balovaptan QD; on Day 7 and Day 14 study drug administration will take place after at least 10 hours of fasting.
- Day 14: the final oral dosing will be followed 1.25 hours later by a 15-minute IV infusion of [¹³C]-labeled balovaptan 0.1 mg.

Cohort 2

Period 1:

- Day 1: a single oral dose of 50 mg balovaptan after at least 10 hours of fasting, followed 1.25 hours later by a 15-minute IV infusion of [¹³C]-labeled balovaptan 0.1 mg.

Period 2:

[figure not shown]
- Day 1 to Day 14: oral doses of 50 mg balovaptan QD; on Day 7 and Day 14 study drug administration will take place after at least 10 hours of fasting.
- Day 14: the final oral dosing will be followed 1.25 hours later by a 15-minute IV infusion of [¹³C]-labeled balovaptan 0.1 mg.

Follow-up

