4.3.2.1 Balovaptan (Oral Administration)

An oral dose of balovaptan 10 mg (Cohort 1) or 50 mg (Cohort 2) will be administered in the morning of Day 1 of Period 1 and each morning of Days 1 to 14 of Period 2. On Days 1 of Period 1 and Days 7 and 14 of Period 2, study drug administration will be after an overnight fast of at least 10 hours, followed by another 4 hours of fasting until lunch. On the other dosing days, study drug administration will take place at least 30 minutes before breakfast. Water will be allowed ad libitum until 1 hour prior to dosing and from 1 hour post dosing, and a maximum of 3 liters a day.

Study drug will be swallowed whole with 240 mL of still water.

4.3.2.2 [¹³C]-Labeled Balovaptan

On Day 1 of Period 1 and on Day 14 of Period 2, a single microdose of [¹³C]-labeled balovaptan 0.1 mg will be administered by a 15-minute constant IV infusion. The IV infusion will start 1.25 hours after administration of the oral dose of unlabeled balovaptan on Day 1 of Period 1 and Day 14 of Period 2.

Details on study drug preparation by the PRA Health Sciences (PRA) pharmacy will be described in the Manufacturing Batch Record, which will be prepared by the PRA pharmacy.

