Appendix 2 Schedule of Pharmacokinetic Blood [REDACTED] Samples

Procedure		Blood sampling for balovaptan and M2, M3 metabolites							Blood sampling for ¹³ C-balovaptan		[REDACTED]	
		Period 1	Period 2							Period 1	Period 2	Period 2
Study Day		1	1	2	7	8	12	13	14	1	14	12
Predose		X	X	X	X	X	X	X	X			
Hours Post Oral Dose	0.25	X										
	0.5	X							X			
	1	X							X			
	1.25	X							X	X ^a	X ^a	
	1.33	X							X	X	X	
	1.5	X							X	X	X	
	1.75	X							X	X	X	
	2	X			X				X	X	X	
	2.25	X							X	X	X	
	2.5	X							X	X	X	
	3	X			X				X	X	X	X ^b
	3.5	X							X	X	X	
	4	X			X				X	X	X	
	4.5	X							X	X	X	
	5	X							X	X	X	
	6	X			X				X	X	X	
	8	X							X	X	X	
	12	X			X				X	X	X	
	16 (P1/D2 or P2/D15)	X (D2)				X			X (D15)	X	X (D15)	
	24 (P1/D2 or P2/D15)	X (D2)							X (D15)	X	X (D15)	
	48 (P1/D3 or P2/D16)	X (D3)							X (D16)	X	X (D16)	
60 (P1/D3 or P2/D16)	X (D3)							X (D16)	X	X (D16)		
72 (P1/D4 or P2/D17)	X (D4)							X (D17)	X	X (D17)		
96 (P1/D5 or P2/D18)	X (D5)							X (D18)	X	X (D18)		
108 (P1/D5 or P2/D18)	X (D5)							X (D18)	X	X (D18)		
120 (D6)	X (D6)											
144 (D7)	X (D7)											
168 (D8)	X (D8)											
192 (D9)	X (D9)											
216 (D10)	X (D10)											

Appendix 2

Schedule of Pharmacokinetic Blood and CSF Samples (cont.)

[REDACTED]; P1 = Period 1; P2 = Period 2.

^a Sample to be taken as shortly as possible prior to start of intravenous infusion.

[REDACTED]

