#### 5.2 Secondary Objectives

- To determine the absolute oral bioavailability of a single dose of 50 mg balovaptan.
- To determine the absolute oral bioavailability of balovaptan after once daily doses of 10 mg or 50 mg for 14 days.
- To characterize the dose- and time-dependency of the PK of oral balovaptan.
- To determine plasma concentrations of [C]-labeled balovaptan, balovaptan, and its metabolites M2, and M3, following a single oral dose of balovaptan 10 mg or 50 mg together with a slow intravenous (IV) infusion of a microdose of [C]-labeled balovaptan.
- To determine plasma concentrations of [C]-labeled balovaptan, balovaptan, and its metabolites M2, and M3, following once daily oral dosing of 10 mg or 50 mg once daily (QD) for 14 days together with a slow IV infusion of a microdose of [C]-labeled balovaptan after the last oral dose.
- To evaluate the safety and tolerability of balovaptan 10 mg QD and 50 mg QD.

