**Table 1: Plasma Parameters**

Parameter	Description	Analyte/Analysis Period	SAS Programming Notes
C max	Maximum plasma concentration. Observed peak analyte concentration obtained directly from the experimental data without interpolation, expressed in concentration units	All analytes	C max from WNL
C trough	Concentration at the end of the dosing interval (tau)	All analytes/ Period 2	The concentration at 24 h calculated in SAS
C last	Last measurable plasma concentration	All analytes	Calculated in SAS
t max	Time to maximum plasma concentration. First observed time to reach peak analyte concentration obtained directly from the experimental data without interpolation, expressed in time units.	All analytes	T max from WNL
AUC 0-last	Area under the concentration-time curve (time 0 to time of last quantifiable concentration).	All analytes/ Period 1	AUC last from WNL
AUC 0-inf	Area under the serum concentration-time curve (time 0 to infinity). Percent extrapolation less than or equal to 20% is required to obtain a reliable AUC inf .	All analytes/ Period 1	AUC INF_obs from WNL If AUC_%Extrap_obs >20% then parameter is not included
AUC 0-24h	Area under the serum concentration-time curve from time 0 to 24 hours post-dose	All analytes/ Period 1 and 2	AUC 0-24 from WNL where partial time =24, if missing for a subject then AUC at nominal time 24 hr from summary file is used for AUC 0-24
λ z	Terminal phase rate constant calculated by linear regression of the terminal log-linear portion of the concentration vs. time curve. Linear regression of at least three points and an adjusted R  greater than 0.70 are required to obtain a reliable λ z .	All analytes	Lambda_z from WNL If adjusted R  ≤ 0.7 the parameter is not estimated
t 1/2	Terminal phase half-life expressed in time units. Percent extrapolation <20% and adjusted R  greater than 0.7 is required to obtain a reliable t 1/2 .	All analytes	HL_Lambda_z from WNL If adjusted R  ≤ 0.7 the parameter is not estimated
t last	Time of last measurable plasma concentration	All analytes	Determined in SAS
R AUC	Accumulation ratio for AUC 0-24h	All analytes	Day 14 AUC 0-24h Period 2/ Day 1 AUC 0-24h Period 1 Calculated in SAS

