### 16.2.2 Pharmacokinetic Parameters

Plasma PK parameters for balovaptan, [C]-balovaptan, M2 and M3, will be estimated using non-compartmental methods with WinNonlin®.

The plasma PK parameters will be estimated from the concentration-time profiles. In estimating the PK parameters, BQL values will be set to zero for the pre-dose PK sample, as well as for all other samples being BLQ and occurring before  $t_{max}$ . For subsequent time points, the result will be set to missing. Actual sampling times, rather than scheduled sampling times, will be used in all computations involving sampling times. If the actual time or dose time is missing, the scheduled time may be substituted in order to calculate the PK parameter.

Descriptive statistics (number of subjects, arithmetic mean, geometric mean, SD, geometric and arithmetic CV, median, min, and max) will be used to summarize the calculated PK parameters by treatment, day and analyte. For  $t_{max}$ , only median, min and max will be presented.

The points to be included in the  $\lambda z$  range will be determined by the pharmacokineticist after inspection of the semi-log concentration-time profiles. At least 3 points will be required to be used and the range should ideally be spread over a time interval representing at least 2 half-lives. The  $C_{max}$  data point will not be included.

Parameters based on  $R^2$  below 0.70 or %AUCextra above 20% will be flagged and excluded from descriptive statistics.

The ratio of geometric means from the microdose IV kinetics with that from the oral dose will be estimated using an analysis of variance (ANOVA) of the natural logarithm transformed clearance (CL and CL/F). A mixed model will be used, separately for the 2 cohorts with the 2 doses of 10mg and 50mg, and will include fixed effects for route (oral or iv) and for day (1 and 14) and a random effect for subject. From this model the least-squares means (LSMeans) for clearance (CL) of [C]-balovaptan iv and for CL/F of oral balovaptan will be presented. The ratios of the LSMeans for the comparison of CL to CL/F (IV/Oral) will be obtained by exponentiating the difference of the LSMeans on the log scale. A 90% confidence interval for the ratios of the treatment means will be calculated.

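### The 20% extrapolation condition on t1/2 in SAP Table 1 caps summarised half-life at about 46-50 h on Day 14 but about 93 h on Day 1, and conflicts with the row's own programming note

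*SAP*

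**What the plan says.** SAP Table 1 gives two instructions for t1/2, for all analytes and with no period restriction. The description column requires "Terminal phase half-life expressed in time units. Percent extrapolation <20% and adjusted R" squared greater than 0.7. The programming note in the same row withholds the value only when adjusted R-squared is 0.7 or less and does not mention extrapolation. The lambda-z row asks for at least three points and the same R-squared limit, and has no extrapolation condition.

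The AUC0-inf row states "Percent extrapolation less than or equal to 20% is required to obtain a reliable AUC" to infinity. There the programming note does code the 20% cut, and the row is limited to Period 1.

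SAP 16.2.2 adds a general rule: parameters based on a low R-squared or with an extrapolated AUC "above 20% will be flagged and excluded from descriptive statistics".

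The sampling schedule (Protocol Appendix 2, SAP Appendix 3) follows balovaptan, M2 and M3 to 216 h after the Period 1 dose. After the Day 14 dose it stops at the row that begins "108 (P1/D5 or P2/D18". [13C]-balovaptan stops at that row in both periods.

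Protocol 1.2.1.1 reports from earlier work that "the mean apparent elimination half-life after the last dose (Day 14) was approximately 46 hours". SAP 5.2.1 names t1/2 among the secondary endpoints, and SAP 5.2 includes the objective "To characterize the dose- and time-dependency of the PK of oral balovaptan".

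**The concern.** Lambda-z and t1/2 carry the same information, yet the description column accepts them on different criteria. The added criterion is not neutral. With a fixed last sample, the extrapolated percentage rises with half-life, so a limit on one is an upper limit on the other. Long half-lives are removed because they are long, not because they are badly estimated.

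For unlabelled balovaptan the last sample is twice as late on Day 1 as on Day 14, so the limit sits at a different half-life on each day. The Day 1 and Day 14 summaries of t1/2 would then describe differently selected subjects. A reader using them for the time-dependency objective could see shorter half-lives after repeated dosing when nothing had changed.

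**Working it through.** The plan gives no figure of its own for the effect of this rule, so there is none to reproduce.

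**Inputs from the documents.** Last sample T = 108 h (Day 14) and 216 h (Day 1); limit 20%; mean Day 14 t1/2 about 46 h; 8 subjects per cohort.

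**Assumptions.** t1/2 is log-normal with CV 20-40%. The documents give no CV for t1/2; the 42% in Protocol 6.1 is for CL/F. Concentrations on Day 1 stay quantifiable well past 108 h; no LLOQ is given.

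**Step 1: the cap.** For a mono-exponential decline the extrapolated fraction is 2^(-T/t1/2). Setting it to 0.20 gives t1/2 = T x ln2/ln5.

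- Day 14: 108 x 0.6931/1.6094 = 46.5 h.
- Day 1: 216 x 0.6931/1.6094 = 93.0 h.
- At t1/2 = 46 h the extrapolated part is 2^(-108/46) = 19.6% on Day 14 and 2^(-216/46) = 3.9% on Day 1.

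**Step 2: other profile shapes.** First-order absorption (ka 0.3 to 2 per h) puts the Day 14 cap at 46.1 to 46.4 h. A distribution phase holding 5% to 30% of single-dose AUC raises it to 46.8 to 50.5 h. The Day 1 cap stays at 91.6 h or higher throughout.

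The distribution phase matters for the higher dose. A mono-exponential 46 h half-life predicts accumulation of (1 - 2^(-336/46))/(1 - 2^(-24/46)) = 3.3-fold, whereas Protocol 1.2.1.1 reports about 4-fold at 12 mg and 2-fold at 52 mg. Under linear kinetics, a fast phase holding 28% of AUC (half-life taken as 4 h) brings accumulation to about 2-fold. With accumulation factors of 3.27 for the slow phase and 1.02 for the fast phase, the Day 14 extrapolation at 46 h is (0.72 x 3.27 x 0.196)/(0.72 x 3.27 + 0.28 x 1.02) = 17.5%. That subject passes, and the cap is near 50 h.

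**Step 3: effect on the summary.** The same true distribution is used on both days. With s = sqrt(ln(1 + CV^2)), cap c and k = ln(c/GM)/s:

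- fraction removed = 1 - Phi(k)
- arithmetic mean of those kept = AM x Phi(k - s)/Phi(k)
- geometric mean of those kept = GM x exp(-s x phi(k)/Phi(k))

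Example: arithmetic mean 46 h, CV 30%, c = 46.5 h. Then s = 0.294, GM = 46/sqrt(1.09) = 44.1 h and k = 0.18. The fraction removed is 42.7%, and the mean of those kept is 36.6 h.

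| 46 h read as | CV | Removed Day 14, cap 46.5 h | Kept mean, Day 14 / Day 1 | Ratio | Removed Day 14, cap 50 h | Ratio |
|---|---|---|---|---|---|---|
| arithmetic mean | 20% | 43.9% | 39.5 / 46.0 h | 0.86 | 30.2% | 0.90 |
| arithmetic mean | 30% | 42.7% | 36.6 / 45.7 h | 0.80 | 33.3% | 0.84 |
| arithmetic mean | 40% | 41.3% | 34.0 / 44.6 h | 0.76 | 34.1% | 0.80 |
| geometric mean | 20% | 47.8% | 39.8 / 46.9 h | 0.85 | 33.7% | 0.89 |
| geometric mean | 30% | 48.5% | 37.2 / 47.6 h | 0.78 | 38.8% | 0.82 |
| geometric mean | 40% | 48.9% | 34.9 / 47.5 h | 0.74 | 41.4% | 0.77 |

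The 93 h cap on Day 1 removes 0% to 3.4%. Kept means and ratios in the table are arithmetic. The mildest case, on geometric means (46 h arithmetic, CV 20%, cap 50 h), is 40.9/45.1 = 0.91. The range is therefore 30-49% removed, or about 2 to 4 of 8 subjects (8 x 0.30 = 2.4; 8 x 0.49 = 3.9), and a shortening of 9-26%. With a true mean of 40 h the same formulas give 4-21%.

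**Step 4: the tracer.** Protocol 4.3.2.2 states "The IV infusion will start 1.25 hours after administration of the oral dose", so the last [13C] sample is 108 - 1.25 = 106.75 h after infusion start on both days. The mono-exponential cap is 106.75 x ln2/ln5 = 46.0 h on each day, and higher with a distribution phase.

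**The case against.** The strongest reply is that the SAP may not intend the cut at all. The t1/2 programming note has no extrapolation condition although the AUC0-inf note does, and AUC0-inf is listed for Period 1 only. The rule in 16.2.2 can also be read as covering only parameters built on extrapolated area. On that reading no bias arises. This stands as a reason for calling the defect a conflict. It does not remove the defect, because the t1/2 description states the condition outright. Nor does the Period 1 limit settle it: the CL and CL/F model in 16.2.2 includes Day 14, and Table 1 derives both from AUC0-inf.

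A second reply is that the effect would be visible and not decisive. Excluded values are flagged, individual values are still tabulated (Tables 14.2.2 and 14.2.4), and the summaries give the number of subjects. No Day 1 to Day 14 ratio or test of t1/2 is planned. Time-dependency also has the accumulation ratios and the day effect in the clearance model. This stands and limits the consequence to the descriptive summaries.

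A third reply is that the limit has a rationale: 20% extrapolation corresponds to log2(5) = 2.3 half-lives observed, close to the ideal in 16.2.2 of a lambda-z range spanning at least 2. That supports flagging short ranges. It does not support excluding values by a criterion tied to the size of the half-life itself.

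A reader might also infer that every subject above 46 h is lost, or that all analytes show the Day 1/Day 14 asymmetry. The documents support neither. With the 2-fold accumulation reported at 52 mg the cap is nearer 50 h, and the tracer has the same last sample on both days.

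**Conclusion.** The point holds as an internal conflict in the acceptance rule for a secondary endpoint. It produces a selection bias if the Table 1 description and 16.2.2 are followed, and none if only the programming note is followed.

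For unlabelled balovaptan the cap is about 46-50 h on Day 14 and about 93 h on Day 1, and the protocol's own mean lies at or near the Day 14 cap. With identical true half-lives on both days, about 30-49% of subjects would leave the Day 14 summary and almost none the Day 1 summary. The apparent shortening would be about 9-26%, or about 4-21% if the true mean is 40 h. The direction follows from the unequal sampling windows; the size rests on the assumed log-normal CV of 20-40%, the profile shape and quantifiable late samples on Day 1.

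M2 and M3 share the sampling schedule, but the documents give no half-life for them, so no size can be stated. [13C]-balovaptan can lose long half-lives on both days without an asymmetry from the schedule. It would be too strong to say that the Day 14 half-lives are discarded: they leave the summary statistics but remain in the individual data. The acceptance rule for t1/2 does not enter the primary endpoint, F after a single 10 mg dose.

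**What to change.** In SAP Table 1, delete the percent-extrapolation condition from the t1/2 description, so that it agrees with its programming note and with the lambda-z row. In SAP 16.2.2, limit the 20% exclusion to parameters that contain extrapolated area: AUC0-inf, CL, CL/F, Vss and F. Accept t1/2 on lambda-z fit (adjusted R-squared, at least three points), and flag, without excluding, values whose fitting range spans less than 2 half-lives.

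Optionally, also report Day 1 t1/2 from samples up to 108 h as a like-for-like sensitivity analysis beside Day 14.

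The cost is SAP wording, plus one further WinNonlin run if the sensitivity analysis is added. No change to sampling is needed. The downside is that some Day 14 half-lives now kept in the summary will be less precise; the flag makes that visible.

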#### Period 2:

[figure not shown]
- Day 1 to Day 14: oral doses of 10 or 50 mg balovaptan QD; on Day 7 and Day 14 study drug administration will take place after at least 10 hours of fasting.
- Day 14: the final oral dosing will be followed 1.25 hours later by a 15-minute IV infusion of [C]-labeled balovaptan 0.1 mg.

[REDACTED]

The target population will be healthy male (at least 4 male subjects enrolled per cohort) and female subjects, aged 18 to 65 years, inclusive, at screening. At least 4 subjects enrolled per cohort should be aged 18 to 50 years, inclusive, at screening.

Figure 1 presents an overview of the study design.

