R Cmax	Accumulation ratio for C max	All analytes	Day 14 C max Period 2/ Day 1 C max Period 1 Calculated in SAS
R Ctrough	Accumulation ratio for C trough	All analytes	Day 14 C trough Period 2/ Day 1 C trough Period 1 (24 h sample on Day 2) Calculated in SAS
F	Absolute bioavailability (oral versus IV in %)	Balovaptan ([  C]- balovaptan)	Calculated in SAS as $F = \frac{AUC_{oral+DIV}}{AUC_{IV+Doral}} * 100$ AUC 0-inf of Balovaptan as AUC oral and AUC 0-inf of [  C]-Balovaptan as AUC IV
CL	Total body clearance (IV administration only) obtained by dividing the total dose of parent drug by its corresponding AUC 0-inf	[  C]-balovaptan	CL_obs from WNL
CL/f	Apparent total plasma clearance of drug after oral administration obtained by dividing the total dose of parent drug by its corresponding AUC 0-inf	balovaptan	CL_F_obs from WNL
V ss	Volume of distribution at steady state (IV administration only)	[  C]-balovaptan	V ss_obs from WNL

Note: AUCs will be calculated using linear up / log down, expressed in units of concentration x time.

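### Day 14 oral F and CL/F rest on AUC0-inf, which at steady state carries drug from 13 earlier doses: multiple-dose F is overstated about 2- to 4-fold, or has no planned input

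*SAP*

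**What the plan says.** - **F.** SAP Table 1 calculates F in SAS as a dose-normalised ratio of areas, using "AUC 0-inf of Balovaptan as AUC oral and AUC 0-inf of" [13C]-balovaptan as the IV area. The row names no period or day.
- **CL/F.** The same table defines it as "Apparent total plasma clearance of drug after oral administration obtained by dividing the total dose of parent drug by its corresponding AUC 0-inf", again with no period limit.
- **AUC0-inf.** The row for "Area under the serum concentration-time curve (time 0 to infinity") assigns the parameter to Period 1 for all analytes. AUC0-24h is assigned to Periods 1 and 2.
- **Objective.** SAP Section 5.2 includes "To determine the absolute oral bioavailability of balovaptan after once daily doses of 10 mg or 50 mg for 14 days".
- **Model.** The mixed model for log CL and log CL/F in SAP Section 16.2.2 "will include fixed effects for route (oral or iv) and for day (1 and 14) and a random effect for subject".
- **Dosing.** The Day 14 profile comes at the end of Period 2: "Day 1 to Day 14: oral doses of 10 or 50 mg balovaptan QD".
- **Protocol.** Section 6.6 ties AUCinf to a single dose and AUC0-24 to the dosing interval at steady state, but gives no formula for F. SAP Section 7.1 reports no changes from the protocol.

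**The concern.** On Day 1 of Period 1 the oral and IV doses are both single doses, so a ratio of AUC0-inf values is a valid F. On Day 14 of Period 2 the labelled microdose is in effect still a single dose, but the oral drug is not. The AUC0-inf of unlabelled balovaptan from Day 14 onwards is the area from dose 14 plus the remaining area from doses 1 to 13, and the formula divides it by one dose. Nothing removes the excess: SAP Section 16.2.2 sets pre-dose values to zero only when they are below the quantification limit. Nor does it cancel against the IV term.

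If the analyst instead follows the Period 1 limit in the AUC0-inf row, Day 14 F and CL/F have no planned input. Day 14 CL of [13C]-balovaptan, a listed secondary endpoint, is then also without a planned area. Neither reading delivers the multiple-dose objective.

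At stake are F at steady state for both dose levels, the objective on time-dependency of the oral PK (accumulation would appear as a fall in CL/F), and the modelled IV/oral ratio, which draws on both days.

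**Working it through.** **Inputs from the documents**

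| Input | Value | Source |
|---|---|---|
| Dosing before and at the Day 14 profile | once daily, 14 doses (13 earlier) | SAP 6.0 |
| Half-life after the last dose | about 46 h | Protocol 1.2.1.1 |
| Accumulation | about 4-fold (12 mg), 2-fold (52 mg) | Protocol 1.2.1.1 |
| Last Day 14 sample | 108 h after the oral dose | SAP Appendix 3 |
| Extrapolation limit | 20% | SAP Table 1, 16.2.2 |
| Sizing | 6 subjects, 35% variability, 90% CI | SAP 6.1 |

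The half-life input reads "the mean apparent elimination half-life after the last dose (Day 14) was approximately 46 hours".

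**Assumptions not in the documents:** linear superposition; first-order absorption with ka of 0.5 to 2 per hour; and, as a sensitivity case, 0 to 40% of the area in a fast phase with a 3 h half-life.

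**1. The plan's own figure.** The only computed figure for this comparison is the precision factor of 1.50. It reproduces: exp(t(0.95, 5 df) × 0.35 × √(2/6)) = exp(2.015 × 0.35 × 0.577) = 1.503. The other entries in Protocol Table 4 come out at 1.418 and 1.593, against 1.42 and 1.59. The plan gives no figure for the Day 14 area.

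**2. Overstatement if AUC0-inf is used on Day 14.** For a mono-exponential profile, the area from dose 14 onwards relative to the area of one dose is (1 − e^(−14·24k)) / (1 − e^(−24k)).

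- k = 0.693/46 = 0.01507 per h, so 24k = 0.3616 and e^(−24k) = 0.6965.
- At full steady state: 1/0.3035 = 3.30.
- After 14 doses: 3.295 × (1 − 0.0063) = 3.27.

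**3. Sensitivity to shape and half-life.**

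- With absorption, AUC0-inf over AUC0-24 after dose 14 is 3.31 to 3.37 for ka of 2 down to 0.5 per hour.
- With up to 40% of the area in the fast phase, the overstatement at 46 h ranges from 2.4 to 3.35. For half-lives of 36 to 56 h it ranges from 2.0 to 3.9.
- Mono-exponential half-lives of 24 h and 57.8 h, those that would produce 2- and 4-fold accumulation, give 2.0 and 4.0 (3.9 after 14 doses).
- The excess does not depend on extrapolation. At 46 h, the area to 108 h alone is 3.274 × (1 − 0.196) = 2.63 times the single-dose area.

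**4. Effect on the reported values.** At 3.3-fold, a true Day 14 F above 1/3.3 = 30% is reported above 100%. The threshold is 50% at 2-fold and 25% at 4-fold. Day 14 CL/F falls to about 30% of its true value at 3.3-fold.

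**5. Effect on the model.** There is no route-by-day term, so with balanced data the IV/oral ratio averages the two days on the log scale. A Day 14 error of size R multiplies it by √R: √3.27 = 1.81 at 46 h, and 1.41 to 2.00 for R of 2 to 4. The 46 h value exceeds the 1.50 precision factor.

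**6. The IV term is sound.** The residue of the first microdose 27 days later is e^(−0.01507 × 648) = 0.00006, below 0.01%.

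**7. The matching area.** In the same simulations, AUC0-24 after dose 14 is 98 to 100% of the single-dose AUC0-inf, so the bias factor becomes about 1.0.

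**The case against.** The strongest reply is that the documents never plan a Day 14 oral AUC0-inf. The SAP row is limited to Period 1, the protocol reserves AUCinf for single doses, and AUC0-24 is planned for Period 2. On this view the defect is an omission that a pharmacokineticist would fill correctly, and the 2- to 4-fold bias arises only if someone ignores the Period 1 limit. It is true that the bias is conditional on that reading. But the F and CL/F rows carry no period limit and name AUC0-inf, and no passage names another area for Day 14. Double programming of the PK parameter dataset would reproduce a specification error, not detect it.

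Other points stand as qualifications:

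- The factor assumes linear PK, whereas the protocol reports time-dependent PK and a more than dose-proportional rise after single doses. A 46 h half-life predicts about 3.3-fold accumulation, not the reported 4- and 2-fold. Accumulation is also not the same quantity as AUC0-inf over AUC0-24 on Day 14, so the range should not be read as 4-fold in one cohort and 2-fold in the other.
- Calling Day 14 IV CL impossible to compute would be too strong. Its row has no period limit and labelled samples run to 108 h, so that part is an inconsistency within the table.
- With only main effects, the model would put part of the error into a day effect shared by both routes. The false time effect specific to CL/F would appear in the descriptive Day 14 against Day 1 summaries.
- The study is exploratory, tests no hypothesis, and its primary endpoint is not touched.

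**Conclusion.** The concern holds. As written, Day 14 oral F and CL/F are either inflated by drug from the 13 earlier doses or have no planned input, so the secondary objective on multiple-dose F is not met under either reading. On the first reading the overstatement of F is about 3.3-fold at the protocol's half-life, and roughly 2- to 4-fold over the half-lives and profile shapes examined. CL/F is understated by the same factor, and each cohort's modelled IV/oral ratio is inflated about 1.4- to 2.0-fold. These sizes rest on linear superposition and are approximate; the direction does not depend on the exact half-life. Individual Day 1 F is unaffected, but the modelled ratio for the 10 mg cohort is not protected. This must be fixed before analysis: a correction made after impossible values appear would be post hoc, and a 2-fold error on a true F below 50% would give a plausible value and could pass unnoticed.

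**What to change.** Amend SAP Table 1 as follows:

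- **F:** define the oral area by period. Period 1 uses AUC0-inf; Period 2 Day 14 uses AUC0-24h. The IV area stays AUC0-inf of [13C]-balovaptan on both days.
- **CL/F:** Period 1 is dose over AUC0-inf; Period 2 Day 14 is dose over AUC0-24h.
- **AUC0-inf:** extend the row to Period 2 for [13C]-balovaptan, so that Day 14 IV CL and F have a stated input.

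State in Section 16.2.2 that the model uses these Day 14 values. The cost is wording in three table rows and one sentence; AUC0-24h for Period 2 is already planned and no new data are needed.

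One limit remains. At a 46 h half-life, the labelled area extrapolated beyond the last sample (106.5 h after the end of infusion) is e^(−0.01507 × 106.5) = 20.1%, right at the 20% exclusion limit. Subjects with half-lives of about 46 h or longer could therefore still lose Day 14 F and CL. That is a separate matter and does not alter the change above, but the SAP should say how such subjects are handled.
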